Significance 1 – Importance and Health Relevance of the Research. PD is a chronic neurodegenerative condition affecting an estimated 40,000 veterans treated within the VHA; it is the most common neurodegenerative disease after Alzheimer's disease.¹⁹ The American Parkinson Disease Association states that nationally nearly 60,000 new cases a year are diagnosed with PD, joining approximately 1,500,000 people and their families in the US that are afflicted with this disease (<http://www.youngparkinsons.org>). About 10-20% of individuals are under age 50 when they develop PD, most are over age 65 at onset (<http://www.youngparkinsons.org>). PD affects not only mobility and gait but is also often associated with cognitive impairment, mood disorders including anxiety and depression, and other "non-motor" effects that often go unrecognized, with adverse consequences. Research has shown that these psychiatric and behavioral disturbances, cognitive symptoms, and other nonmotor difficulties such as pain, gastrointestinal, and lower urinary tract symptoms are as troubling or often more troubling when compared to motor symptoms.^{1, 20}

While evidence-based treatments exist that are well-documented to improve outcomes for veterans with PD, there are substantial gaps in PD care within and outside of VA. In our previous research, for example, a sample of veterans with PD receiving care at three VA Healthcare Systems in the southwestern US were interviewed. Results indicated that veterans with PD reported receiving education and counseling about care issues rated important by a national panel of PD experts only 49% of the time overall, ranging from 34% for counseling on driving safety to 70% for understanding their PD medications (personal communication: [name] and [name]). Of those with a care need in the prior 6 months, 46% reported this need was unmet (personal communication: [name] and [name]). Sizeable room for improvement was identified for these veterans' needs for rehabilitation, mental health care, and home health care. Medical record reviews conducted in VA facilities in two US regions, found low adherence rates for multiple established quality of care indicators for PD,^{15,17} including low rates of assessments of falls (51%; n/N=139/271) and depression (60%; n/N=163/271), and an association of non-white race with lower rates of depression treatment.^{14,15,17}

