Research Design and Methods 1 – Overview of Study Design. The proposed study is a multi-site, single-blinded, patient-level randomized-controlled trial of a nurse-coordinated care management intervention for Parkinson’s disease (“CHAPS”) relative to care as usual. Study outcomes will be measured by (1) surveys administered to veterans, to occur at baseline and at 6, 12, and 18 months (and 24 months for the first 204 enrollees), and (2) medical record abstraction in year 4. The primary outcome is adherence to evidence-based guidelines for PD care. Secondary outcomes include: patient health-related quality of life, self-efficacy, and perceptions of care quality. All outcomes will be assessed using intention-to-treat analyses. Three hundred veterans from across five VISN 22 VAs - Greater Los Angeles, Las Vegas, Loma Linda, Long Beach and San Diego - will be recruited and enrolled to enable a final analytic sample (accounting for attrition) of 266. Enrollees will be randomized in a 1:1 ratio to either receive the CHAPS intervention or care as usual. CHAPS intervention components include (1) periodic, structured telephone assessments administered by a nurse care manager specially trained in PD care management at each facility, to identify unrecognized problems (CHAPS Assessment Tool Appendix 1), (2) evidence-based algorithms and protocols to guide care coordination by the nurse care manager (CHAPS Nurse Care Management Manual, Appendix 2), (3) a standalone electronic Microsoft Access database for each nurse care manager, to enable automated triggers of care management and coordination activities, for tracking timeliness of activities (including ‘overdue’ activities) across a registry of his/her patients, and to enable efficient transfer of template clinical reports and care plans (see overall care plan “CHAPS Care Tracker” in Appendix 3) into CPRS (4) veteran and – where appropriate - family involvement in care planning (“My Action Plan” Appendix 4), (5) incorporating self-management tools including My HealtheVet, Patient Education Resource Center and a PD-specific, self-management toolkit including patient notebooks (Siebens Health Care Notebooks) to enrich communication with providers; and an information binder and logs from Davis Phinney (<http://davisphinneyfoundation.org/living-pd/victory-counts>) and; (6) proactive referral mechanisms both within VA and to Parkinson’s disease-specific community resources as needed (referral template in Appendix 5) provide the Veteran has signed the HIPAA granting permission to provide PHI to community organizations as part of the referral process. Outcome variables will be collected by a research assistant interviewer blinded to trial arm status, with three waves of measurement occurring at 6, 12, and 18 months (and 24 months for the first 204 enrollees) after baseline measurement (evaluation survey, Appendix 6).

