Health services utilization. Physician visits, emergency department visits, hospital admissions, nursing home admissions (distinct from respite care), home care services, and pharmacy data will be obtained from the VISN-22 Data Warehouse, which includes admissions to non-VA hospitals if the VA reimburses those hospitals for the care delivered. We will include home care services to examine whether there are fewer hospitalizations in the intervention group and thus less need for post-acute home care, and we will examine pharmacy costs to assess whether increased provider contact in the intervention arm results in an increase in pharmacy costs.

Intervention Activities' Time: Start Up and Maintenance. Estimates of start up and maintenance costs will be generated in part from intervention activity logs, as recorded at various sampled dates by the nurse care managers in a Nurse Activities Log, and by an Intervention Activities Log Tool. These logs track the frequency and the time required for care management activities performed by the nurse care managers as well as intervention-related activities (preparing intervention materials for veterans) performed by any other staff assistants.

Research Design and Methods 6 - Recruitment and Enrollment/Consent Processes. A list of eligible veterans with at least two ICD-9 diagnostic codes for PD (332.0) in the administrative data will be generated through a query of the Data Warehouse for VISN 22 from October 1, 2010-\ through 12/31/2014 or until full enrollment is achieved.²⁷ An electronic version of that list will be securely transferred from the VA GLA Data Warehouse programmer who generates it to the study RA, who will sort veteran's names by the provider who has seen the patient at those visits. A CHAPS nurse care manager will review, in CPRS, the VHA Data Warehouse query results received from the VHA Data Warehouse programmer. If there are multiple providers for a given veteran, the provider to whom the name will be sorted will be prioritized in the following way: first, a movement disorder neurologist; second, a general neurologist; and third, a primary care physician. Each provider will be asked to vet his/her respective list, removing any veteran's name that is deemed inappropriate to contact about the study, and having the opportunity to add names of potentially eligible subjects to the list

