- HIPAA Authorization (VA Form 10-5345)
- Copy of CHAPS Report of Assessment Summary (prepared by the CHAPS Nurse care Manager) mailed to participant if requested,
- CHAPS Self-assessment summary print out from kiosk that the veteran can give to his/her provider at a movement disorders clinic visit,
- Copy of veteran's self management care plan "My Action Plan" (intervention arm) mailed to participant
- Referral to agencies outside the VA

We will establish a 4-member multidisciplinary centralized data safety monitoring board (DSMB) that will include two Movement Disorder Specialists, [name] and [name], a Geriatrician, [name] and a Parkinson's disease nurse specialist, [name]. The DSMB will be chaired by [name]. This board will meet prior to patient enrollment and then every 6 months to evaluate any adverse effects related to recruitment, enrollment, interview process and the care management intervention.

Care management, is an enhancement of usual care (i.e. usual care consists of all treatment options available to a provider to individualize a patient's care). The care management intervention processes in this study include asking questions to identify problems and unmet needs, some of which are often under-recognized and under-reported in usual care. Intervention care managers will provide information and support, and link veterans with appropriate providers and social services to address and manage these issues. Although we do not anticipate any breaches of confidentiality in this study, human error may result in accidental breaches of confidentiality. This risk will be minimized through rigorous IRB and ISO approved privacy confidentiality and data security procedures. Therefore, we foresee no potentially reportable adverse events related to the care management intervention in this minimal risk study except for possible breaches in confidentiality. Each site will convey any reportable events to the study PI at GLA who will then report these events to the Central IRB and our project DSMB.

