6. **Environmental context and organization support:** Health system and community organization characteristics, other VA care management practices, use of information systems; key leadership support, organizational resource commitment
7. **Veterans’ impressions:** Veteran’s assessment, veteran’s care plan, interactions with the nurse, community organizations, VA social services, use/usefulness of MyHealtheVet, etc.

We will employ a formal card sort approach to theme analysis of the interviews with veterans.⁵⁷ We will organize implementation barrier notes and items from meeting minutes into an excel spreadsheet. In both instances, Drs. [name], [name], and [name] will meet together to come to consensus on sorting the text segments into categories/themes.

Specific Aim #2b. Cost Assessment: Using data collected from the Activity logs and itemized start-up costs, we will estimate separately both fixed and variable start-up and implementation costs of the intervention. Total costs for the intervention implementation will be calculated, broken down as technical assistance costs borne by the research team and implementation costs attributable to clinical staff.

Specific Aim #2b. Health Services Utilization: We will aggregate and compare health services utilization costs between the two study arms. The average cost per patient will be generated based on the administrative data and augmented by selective self-reported healthcare use from the telephone survey. We will calculate the costs associated with health services utilization in the 12 months preceding intervention and during the 18 months of the intervention. Utilization will include physician and emergency room visits, hospital admissions, nursing home admissions, home care services, and pharmacy data. We will determine the units of each service utilized per patient and apply standard unit costs from data costs of VA patient care encounters from

the VA Health Economics Resource Center (HERC). More information on the methods used by HERC to calculate average cost data can be found at: http://www.herc.research.va.gov/methods/methods_cost_ac.asp. The total cost of each participant will be examined between intervention and usual care using a two-sample t test and multivariate regression. Because of potential imbalances associated with the high costs of end-of-life care, we will conduct sensitivity analysis excluding participants who died during the study period.

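### The undivided home-care total cannot show whether post-acute home care fell; admissions answer the hospitalization question, but post-acute use needs its own count

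*Combined protocol and SAP*

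**What the plan says.** Research Design and Methods 5, Other Variables (Health services utilization) gives the reason for collecting home care: the study will "include home care services to examine whether there are fewer hospitalizations in the intervention group and thus less need for post-acute home care". The variables there are "Physician visits, emergency department visits, hospital admissions, nursing home admissions (distinct from respite care), home care services, and pharmacy data", taken from the VISN-22 Data Warehouse. The Health Services Utilization paragraph of Research Design and Methods 6 repeats the list.

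The analysis text, Specific Aim #2b, Health Services Utilization, keeps home care as a single item: "Utilization will include physician and emergency room visits, hospital admissions, nursing home admissions, home care services, and pharmacy data". On counting it says "We will determine the units of each service utilized per patient and apply standard unit costs". The only between-arm test stated there concerns cost: "The total cost of each participant will be examined between intervention and usual care using a two-sample t test and multivariate regression".

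On what CHAPS does, Research Design and Methods 1 lists "proactive referral mechanisms both within VA and to" community resources among the intervention components. Data Management and Quality Control says care managers will "link veterans with appropriate providers and social services to address and manage these issues". Significance 5 expects that the program may cut emergency visits and avoidable admissions, and that it will connect patients with VA and community resources. Significance 1 reports that, in earlier work with veterans, there was considerable room to improve on "needs for rehabilitation, mental health care, and home health care".

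**The concern.** The stated question is about one component, home care that follows a hospital stay. The planned variable is the sum of that component and all other home care. By the protocol's own account, CHAPS could act on the two in opposite directions: fewer admissions would lower post-acute home care, while finding unmet needs and linking veterans to services could raise home care begun in the community.

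If both happen, the total may show no difference or an increase although post-acute use fell. A lower total would not by itself show that fewer admissions were the cause. The sentence that introduces home care already allows for an upward effect on pharmacy costs through more provider contact, but does not carry that reasoning over to home care.

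At stake is one descriptive question under Aim 2b, which is meant to inform VA leadership about the value of the program.

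**Working it through.** **The plan's own figure.** There is none to reproduce. The documents give no rate for admissions, for home care after discharge, or for home care begun by referral.

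**What each planned variable can answer.**

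| Question | Planned variable | Answered? |
|---|---|---|
| Fewer hospitalizations? | Hospital admissions, both arms | Yes, directly |
| Less post-acute home care? | Home care, one category | No, mixed with other home care |
| Net cost offset to VA? | Total cost, including all home care | Yes, the sum is right |

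**Can the two effects cancel?** Every rate below is an assumption.

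*Illustration A, episodes per 100 patients.*
- Usual care: 30 admissions, 40% followed by home care, gives 30 × 0.40 = 12. With 10 other episodes the total is 22.
- CHAPS with 20% fewer admissions: 24 × 0.40 = 9.6, a fall of 2.4.
- A rise in other episodes from 10 to 12.4 (2.4 / 10 = 24%) returns the total to 22.

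*Illustration B, episodes per 100 patients.*
- Usual care: 40 × 0.30 = 12. With 15 other episodes the total is 27.
- CHAPS with 25% fewer admissions: 30 × 0.30 = 9, a fall of 3.
- A rise in other episodes from 15 to 18 (3 / 15 = 20%) returns the total to 27.

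*Break-even in visits.* Let h be admissions per patient, r the relative reduction in admissions, u the post-acute visits per admission, f the share of the intervention arm newly linked to home care, and v the visits per newly linked patient. The net change per intervention patient is −h·r·u + f·v, which is zero at f = h·r·u / v. The planned arm size of 150 is from Research Design and Methods 6 (Randomization).

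| h | r | u | v | Post-acute fall, h·r·u | Break-even f | Of 150 |
|---|---|---|---|---|---|---|
| 0.3 | 10% | 10 | 20 | 0.3 | 1.5% | about 2 |
| 0.6 | 20% | 10 | 10 | 1.2 | 12% | 18 |
| 1.0 | 30% | 20 | 10 | 6.0 | 60% | 90 |

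The first and last rows are the extremes over h from 0.3 to 1.0, r from 10% to 30%, and (u, v) of (10, 10), (10, 20) or (20, 10). Cancellation is arithmetically possible. The width of the range shows that the documents do not fix its size.

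**Can post-acute use be inferred from admissions alone?** Only if home care per discharge is the same in both arms. The CHAPS management text in Research Design and Methods 2 plans an alert to the nurse care manager when an intervention patient is admitted to a VA hospital. That could change home care per discharge in one arm only. In Illustration A, if the share of discharges followed by home care rose from 40% to 12 / 24 = 50%, post-acute episodes would stay at 12 although admissions fell from 30 to 24. Admissions and post-acute home care therefore have to be measured separately and read together.

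**The case against.** The strongest answer is that the important half of the question does not depend on home care. Admissions are a separate item from the same source for both arms, and in both illustrations they visibly fall. A reader might infer that leadership could not tell successful referral from a failure to prevent admissions. The documents do not support that: the admissions count shows whether admissions fell. This part of the objection stands fully.

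Three further points stand:

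- **No reading rule.** A reader might infer that the plan would take an unchanged home-care total as proof of unchanged post-acute need. No section states such a rule, or a hypothesis or test for home care alone.
- **Home care has another use.** It is a component of cost offset, and for that the net total is correct, whatever started the care.
- **The referral route is inferred.** A reader might infer that CHAPS is expected to raise home care. No section says that CHAPS refers veterans to home care; the referral and linking text and the earlier unmet need make a rise plausible, not established. For non-VA care, the Data Warehouse description mentions only admissions that VA reimburses, so home care from community agencies may not enter the total. That would weaken the offset.

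A post-discharge window is also imperfect. Because the admission alert covers intervention patients only, home care arranged by the nurse after discharge would fall inside the window in that arm, so the split can still mix referral with post-acute need.

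What the objection does not remove is the post-acute half. The protocol poses that question, and neither admissions nor the undivided total answers it.

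**Conclusion.** The point holds in limited form. Admissions by arm answer whether there were fewer hospitalizations. The undivided home-care total does not answer whether post-acute home care fell, because a plausible rise in other home care could mask or reverse a fall. The size is unknown: the illustrations rest wholly on assumed rates and show possibility, not likelihood.

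The conclusion rests on two readings of the text: that linking and referral can lead to VA-recorded home care, and that home care stays undivided in the analysis, as the sections on variables, data collection and analysis all list it. Nothing here touches the primary or secondary outcomes, the sample size or the total-cost comparison. This is a minor improvement that lets the trial answer a question it sets itself.

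**What to change.** In Research Design and Methods 5 (Health services utilization) and in Specific Aim #2b (Health Services Utilization):

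1. Name the comparison of hospital admissions by arm as the direct answer on hospitalizations.
2. Before analysis, define post-acute home care as episodes that start within a fixed window (for example, 30 days) after a VA or VA-paid discharge, using service dates in the planned Data Warehouse query.
3. Report post-acute home care per randomised participant by arm, beside admissions, and report other home care separately.
4. Also report post-acute episodes per discharge by arm, descriptively, because the admission alert may change home care per discharge in the intervention arm only.
5. Keep the sum of all home care in the total-cost comparison.

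**Cost.** One derived variable and a few lines in the utilization table, with no new data source. The documents do not say that the extract carries home-care start dates. Counting use within set periods around enrollment implies dated records, but this should be confirmed when the query is written.

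**Downsides to state.** Any cut-off misclassifies some episodes. The misclassification may differ by arm because of the alert, and step 4 makes that visible without removing it. Home care not recorded in the Data Warehouse is missed in both categories.
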